1.2 Previous Nonclinical and Clinical Trial Experience in Tc 99m Tilmanocept

A detailed evaluation of nonclinical evaluations from subcutaneous (SC) and IV routes of administration, clinical pharmacokinetics (PK), clinical efficacy, and clinical safety of Tc 99m tilmanocept can be found in the accompanying Investigator’s Brochure supplied by Navidea Biopharmaceuticals, Inc.

1.2.1 Clinical Pharmacokinetics (IV)

Pharmacokinetics was evaluated in IV administered Tc 99m tilmanocept in the Phase 1 and 2 trial NAV3-21 (NCT02865434). In this trial, 12 subjects (6 RA/6 healthy control [HC]) were administered the maximum dose of 400 mcg tilmanocept radiolabeled with 10 mCi of Tc 99m, and urine and blood data were non-compartmentally modeled to assess potential differences in drug distribution and elimination by disease group (active RA vs. HC).

Subject-level whole blood PK parameters were assessed between HC subjects ($n = 6$) and subjects with active RA ($n = 6$) including mean maximum concentration (C_{max}), mean area under the concentration-time curve (AUC_{0-t}), mean area under the concentration-time curve extrapolated to infinity ($AUC_{0-\infty}$), mean clearance, mean half-life ($t_{1/2}$), and mean elimination rate constant (λ_z) to evaluate potential differences between disease groups ([Table 2](#)). The

geometric mean of whole blood clearance was 26.5 mL/min for HC subjects and 24.8 mL/min for RA patients.

Table 2 Whole Blood PK Parameter Summaries by Group

Group	Statistic	Clearance (mL/min)	AUC(0-t) (min*nCi)	AUC(0-∞) (min*nCi)	Cmax (nCi)	T1/2 (min)
HC	n	6	6	6	6	6
	Mean	27.3	235258.0	370580.1	1244.2	759.0
	Std Dev	7.36	50010.28	92535.92	500.36	134.20
	CV%	26.9	21.3	25.0	40.2	17.7
	Geometric Mean	26.5	230853.1	360357.6	1155.5	749.3
	Lower 90% CI	21.26	193698.75	290005.04	809.55	648.36
	Upper 90% CI	33.04	275134.27	447777.17	1649.33	865.85
RA	n	6	6	6	6	6
	Mean	25.5	268110.7	396026.4	2043.8	719.1
	Std Dev	6.18	61667.51	101351.07	1211.86	138.10
	CV%	24.3	23.0	25.6	59.3	19.2
	Geometric Mean	24.8	262309.5	385984.3	1761.9	707.4
	Lower 90% CI	20.11	217187.41	315475.79	1078.28	598.97
	Upper 90% CI	30.59	316806.03	472251.44	2878.94	835.46

Similarly, subject-level urinary PK parameters including maximum rate, AUC_{0-t}, or percent recovered were assessed for HC subjects (n = 6) and subjects with active RA (n = 6) to evaluate potential differences between disease groups (Table 3). The geometric mean of urine percent recovered was 7.4% in HC subjects and 6.7% in RA subjects.

Table 3 Urine PK Parameter Summaries by Group

Group	Statistic	Percent Recovered ^a	AUC(0-t) (h*nCi)	Max Rate (nCi/h) ^b
HC	n	6	6	6
	Mean	7.6	1468788.9	949280.7
	Std Dev	2.07	432723.27	236916.28
	CV%	27.2	29.5	25.0
	Geometric Mean	7.4	1411786.8	924858.6
	Lower 90% CI	5.84	1088888.09	752742.08
	Upper 90% CI	9.28	1830437.75	1136329.94
RA	n	6	6	6
	Mean	6.9	1384642.0	841331.0
	Std Dev	1.74	313600.65	227308.94
	CV%	25.2	22.6	27.0
	Geometric Mean	6.7	1355137.9	817282.6
	Lower 90% CI	5.46	1123310.11	659111.71
	Upper 90% CI	8.33	1634810.07	1013410.74

^a Percent recovered is the cumulative amount of radioactivity divided by the dose and multiplied by 100.

^b Maximum observed excretion rate, calculated as (radioactivity*volume)/(end time – start time).

A comparison of the PK parameters in HCs and subjects with active RA does not reveal any apparent differences in the elimination of radioactivity from the body.

1.2.2 Clinical Efficacy

1.2.2.1 NAV3-23 (SC)

This was an open-label, multicenter study of Tc 99m tilmanocept by SC administration in HCs and in subjects with active RA. Tilmanocept was administered SC at 1 of 2 mass doses: [1] 50 mcg (Cohorts 1 & 3), or [2] 200 mcg (Cohorts 2 & 4). Both mass doses were radiolabeled with 2 mCi of Tc 99m. A total of 18 subjects were enrolled and evaluated (9 active RA, 9 HC). Imaging was performed 60 ± 15 minutes and 180 ± 15 minutes post-injection. The following performance conclusions were drawn upon study completion:

- Based on data from this study and parallel pathology studies, Tc 99m tilmanocept localizes to activated macrophage-infiltrated joints at doses of 50 µg and 200 µg radiolabeled with 2.0 mCi (74.0 MBq) by SC administration.
- Across all combined RA subjects, swollen/tender joints demonstrating the highest proportions of localization include the wrists and knees.
- Based on qualitative image evaluation, Tc 99m tilmanocept does not show differences in localization between 2 to 3-hour and 4 to 6-hour planar imaging within dosing groups.
- Tc 99m tilmanocept demonstrates a greater frequency of localization to swollen/tender joints at 200 mcg/2.0 mCi than 50 mcg/2.0 mCi.

- There is an overall lack of concordance between qualitative observation of Tc 99m tilmanocept localization to swollen/tender joints identified in DAS28 joint count assessment. Swollen/tender joints did not appear to be reliable predictors of presumed abnormal activated macrophage infiltration and overall disease progression when used as an isolated diagnostic system.
- Increased tilmanocept mass dosing, increased Tc 99m specific activity, and other routes of administration may enhance localization and anatomic delineation in tilmanocept-positive joints of RA patients.
- The potential for using Tc 99m tilmanocept to delineate macrophage infiltration in RA-affected joints may allow for earlier RA-specific treatment beyond the current standard of care ACR/EULAR criteria.

1.2.2.2 NAV3-21 (IV)

This was an open-label, multicenter, dose-escalation safety with PK and dosimetry study of Tc 99m tilmanocept by IV administration in HCs and in subjects with active RA. Thirty-nine subjects were enrolled. A total of 27 subjects with active RA were enrolled to Groups 1 to 9 in the dose escalation phase. Group 10 consisted of 6 HCs (3 female and 3 male), and Group 11 consisted of 6 subjects with active RA (3 female and 3 male). Tilmanocept was administered IV at 1 of 3 mass doses: 50 mcg, 200 mcg, or 400 mcg. Within each mass dose group, tilmanocept was radiolabeled with 1 of 3 Tc 99m doses: 1 mCi, 5 mCi, or 10 mCi. Subjects in Groups 10 and 11 received maximum dose of 400 mcg/10 mCi. Imaging was performed 60 ± 15 minutes and 180 ± 15 minutes post-injection. Clinical efficacy conclusions for this study are still under review.

1.2.3 Clinical Safety

1.2.3.1 NAV3-23 (SC)

The NAV3-23 (NCT02683421) safety evaluation included all trial subjects injected with Tc 99m tilmanocept (N = 18). The AE monitoring was performed from the time of dose administration until completion of onsite safety assessment. There was 1 AE that was possibly related to, and 1 AE that was probably related to Tc 99m tilmanocept. However, there were no AEs that led to trial discontinuation, and no serious adverse events (SAEs) were observed. There were no deaths on trial.

1.2.3.2 NAV3-21 (IV)

The primary safety endpoint of the NAV3-21 study was evaluated by examining the incidence of AEs, changes over time in clinical laboratory tests, physical exams, electrocardiogram (ECG) parameters, and vital signs. The safety evaluation included all subjects who were enrolled in the study and administered Tc 99m tilmanocept (n = 39). There were no Tc 99m tilmanocept related AEs. There were no deaths during the trial, no SAEs, and no AEs that led to discontinuation from the trial.

2 STUDY OBJECTIVES

2.1 Primary Objectives

The primary objectives of this study are:

- Assessment of the relationship between joint-specific tilmanocept uptake value (TUV_{joint}) and synovial anatomic pathology.
- IHC assessment of macrophage expression of the CD206 receptor.

2.2 Secondary Objectives

The secondary objectives of this study are:

- Assessments of CD68 and CD163 receptor expression levels through IHC microscopy.
- Classification of synovial anatomic pathology as
 - Lympho-myeloid
 - Diffuse myeloid
 - Pauci-immune fibroid

2.3 Exploratory Objectives

The exploratory objectives of this study are:

- Determine the relationship between TUV_{joint} and mRNA expression profiles of CD68, CD163, and CD206 as determined by RNA sequencing (RNA-seq).
- Determine the relationship between TUV_{joint} and the number, size, and intensity of CD68, CD163, and CD206 as determined by (optional) flow cytometry.
- Evaluate synovial expression of CD3, CD20, CD55, and TE-7 and CD206 in synovial tissue biopsy specimens.
- Assessment of the relationship between TUV_{global} and synovial anatomic pathology.

2.4 Safety Objective

The safety objective of this study is:

- Evaluate safety through the examination of adverse event (AE) incidence, physical examination findings, and changes over time in laboratory tests, electrocardiograms (ECGs), and vital signs.

3 INVESTIGATIONAL PLAN

3.1 Overall Study Design and Plan

This is a phase 2b, open-label, multicenter, multinational, non-randomized, single-dose study designed to assess the relationship between quantitative Tc 99m tilmanocept planar imaging and synovial histopathology in subjects clinically diagnosed with RA. This study will take place in up to 10 centers in the US, UK, and EU.

Subjects will undergo an imaging assessment of the bilateral hands and wrists followed by an ultrasound-guided synovial biopsy of a select joint at a subsequent visit. Tissue samples from the synovial biopsy procedure will be used for 2 mandatory anatomic pathology evaluations, [1] IHC and [2] RNA-seq, with optional flow cytometry, to provide quantitative and semi-quantitative information regarding joint-specific disease activity. Results from each of the 3 anatomic pathology evaluations will be correlated with TUV_{joint} on planar imaging to mechanistically assess the relationship between synovial anatomic pathology and TUV_{joint} .

The Schedule of Events ([Appendix 1](#)) contains a list of all study procedures and time points. Study activities are described in detail in [Section 7](#).

3.2 Justification for Study Design and Population

This study is designed to evaluate the correlation between TUV_{joint} and the number and area fraction of CD206 expression as determined by IHC assessment in the synovium of subjects clinically diagnosed with RA who are not receiving anti-rheumatic treatment or who are on stable anti-rheumatic treatment. The ability of Tc 99m tilmanocept imaging to detect and discriminate RA pathotypes is being evaluated in these subjects with the goal of supporting personalized therapy. A complete rationale for evaluating Tc 99m tilmanocept in this subject population is discussed in [Section 1.1](#).

3.3 Protocol Adherence

Strict adherence to all specifications outlined in this protocol is required for all aspects of the study conduct; the investigator may not modify or alter the procedures described in this protocol. If protocol modifications are necessary, all alterations that are not solely of an administrative nature require a formal protocol amendment for the involvement of Institutional Review Board(s) [IRB(s)] or Independent Ethics Committee(s) [IEC(s)].

If an investigator has deviated from the protocol to eliminate an immediate hazard to subjects or for other inevitable medical reasons, the investigator shall document all such deviations, including the reasons thereof, and submit the document to the sponsor and the IRB or IEC as applicable.

3.4 Study Duration and Dates

Subjects will be “on study” for up to 45 days depending on the screening window (up to 30 days).

4 STUDY POPULATION SELECTION

4.1 Study Population

This study will evaluate subjects clinically diagnosed with RA who are on stable therapy.

4.2 Inclusion Criteria

Each subject must meet the following criteria to be enrolled in this study.

1. The subject has provided written informed consent with HIPAA (Health Information Portability and Accountability Act) or equivalent authorization before the initiation of any study-related procedures.
2. Women and men of reproductive potential must use adequate birth control measures (e.g., abstinence, oral contraceptives, intrauterine device, barrier method with spermicide, or surgical sterilization) for the duration of the study.
3. The subject is at least 18 years of age and was \geq 18 years of age at the time of RA diagnosis.
4. The subject has RA as determined by the 2010 ACR/EULAR Classification Criteria (score of \geq 6/10 at or before screening).
5. The subject has a DAS28 of \geq 3.2 (includes the C-reactive protein [CRP] test and visual analog scale [VAS]).
6. Subjects receiving traditional DMARDs must have been on therapy for \geq 90 days and at a stable dose for \geq 30 days prior to the first imaging visit (Day 0).
7. If the subject is receiving bDMARD or janus kinase (JAK) inhibitor therapy, they have been at a stable dose $>$ 60 days prior to the imaging visit (Day 0). bDMARD therapy should not be administered less than 4 days prior to the imaging visit.
8. If the subject is receiving NSAIDs or oral corticosteroids, the dose has been at a stable dose for \geq 28 days prior to imaging. The corticosteroid dose should be \leq 10 mg/day of prednisone or an equivalent steroid dose.
9. The subject has a hand or wrist joint with a minimum ultrasound gray-scale synovitis score of 2 (range 0 to 3).

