7.1.1 Visit 1, Screening (Day -30 to Day -1)

- Preliminary review of inclusion and exclusion criteria
- Signed informed consent for study participation
- Allocation of unique subject number; this number will be used to document the subject data in the case report forms (CRFs) and enrollment log
- Demography – date of birth, gender, race
- Medical and surgical history – all relevant prior medical and surgical conditions will be recorded in the CRF. Documented medical conditions will also note the month and year of onset if the condition is still active.
- Concomitant medications (administered within 30 days prior to Tc 99m tilmanocept administration); RA concomitant medications administered within 6 months prior to Tc 99m tilmanocept administration will be recorded.
- Vital signs (body temperature, heart rate, blood pressure, and respiratory rate after at least 1 minute in a resting position)
- Physical examination will include an assessment of height, weight and an examination of general appearance, skin, eyes, ears, nose, throat, head and neck (including thyroid), lungs, heart, abdomen, lymph nodes, musculoskeletal, and nervous system. Any clinically relevant finding is to be documented as a baseline finding. Physical exams that are conducted as standard of care prior to signing informed consent may be used if they are performed within 30 days of Tc 99m tilmanocept administration.
- Clinical laboratory tests – study subjects will have blood obtained for hematology, chemistry, and an RA panel (see [Table 5](#))
- Urine collection for routine analysis
- Urine pregnancy test for women of child-bearing potential. Females of child bearing potential are defined as women that are not surgically sterile (hysterectomy or bilateral oophorectomy) nor postmenopausal for at least 1 year prior to screening. Women who are not of childbearing potential will not require a pregnancy test.
- RA Evaluations:
 - Swollen and tender joints as established by the 2010 ACR/EULAR Classification Criteria and DAS28 will be identified and documented during physical examination.

- An ultrasound of the hands and wrist joints will be obtained to assess synovitis. Subjects must have at least 1 joint with a minimum gray-scale synovitis score of 2 (range 0 to 3) to be eligible for the study.
- Assessment of AEs

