7.1.2 Visit 2, Tc 99m Tilmanocept Administration and Imaging (Day 0)

Pre-Tc 99m Tilmanocept Administration

The following procedures will be completed for all subjects on the day of injection prior to the administration of Tc 99m tilmanocept:

- A urine pregnancy test for women of child-bearing potential. Females of child bearing potential are defined as women that are not surgically sterile (hysterectomy or bilateral oophorectomy) nor postmenopausal for at least 1 year prior to screening. Women who are not of childbearing potential will not require a pregnancy test.
- Assessment of AEs
- Concomitant medication review
- ECG (see [Section 8.7.3](#)) within 30 minutes prior to administration of Tc 99m tilmanocept
- Vital signs after at least 1 minute in a resting position (body temperature, heart rate, blood pressure, and respiratory rate) within 30 minutes prior to administration of Tc- 99m tilmanocept

Tc 99m Tilmanocept Administration

IV administration of Tc 99m tilmanocept will be at study time 00:00. The preferred site of IV placement will be the left or right antecubital vein. The filled syringe will be connected to the catheter for a slow push injection. At the completion of the injection, a 10-mL sterile normal saline flush will be administered. The IV administration will be performed in the Nuclear Medicine Department by an onsite Certified Nuclear Medicine Technologist or Nuclear Medicine Physician. Subjects will be continuously monitored for AEs.

0 to 30 Minutes Post-Tc 99m Tilmanocept Administration

- Assessment of AEs
- ECG (completed before vital signs)
- Vital signs after at least 1 minute in a resting position (body temperature, heart rate, blood pressure, and respiratory rate)

60 to 75 Minutes Post-Tc 99m Tilmanocept Administration

- Assessment of AEs
- Image acquisition: Static gamma camera scan of the bilateral hands and wrists
- Clinical Labs (at conclusion of the imaging session)

7.1.3 Visit 3, Follow-up Telephone Safety Assessment (24 to 72 hours post-Tc 99m tilmanocept administration)

- Review of concomitant medications
- Assessment of AEs

7.1.4 Visit 4, Synovial Tissue Biopsy (Day 3 to 7 post-Tc 99m tilmanocept administration)

- Ultrasound assessment of synovitis
- Ultrasound-guided synovial tissue biopsy of selected joint in accordance with [Table 4](#)
- AE assessment
- Review of concomitant medications

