8.5 Synovial Biopsy

8.5.1 Joint Selection

All subjects will undergo a synovial biopsy of a selected hand or wrist joint. All joints selected for biopsy will be required to have an ultrasound gray-scale synovitis score of ≥ 2 (range 0 to 3). In instances where more than 1 joint is qualified for biopsy, the candidate joint will be selected based on TUV_{joint} (as described in [Table 4](#)).

Table 4 Biopsy Selection Options

Option	Description
1	The subject has only 1 MCP joint or wrist joint with an ultrasound gray-scale synovitis score of ≥ 2 . This joint will be selected for biopsy.
2	The subject has 2 or more MCP and/or wrist joints with an ultrasound gray-scale synovitis score of ≥ 2 . The joint for biopsy will be selected based on evaluation of corresponding TUV_{joint} . In the first subject with multiple qualifying joints, the joint with the highest TUV_{joint} will be selected; in the second subject with multiple qualifying joints, the joint with the lowest TUV_{joint} will be selected. Selection will proceed in this fashion, alternating between highest and lowest TUV_{joint} .

The ultrasound assessment for synovitis score should take place at screening and prior to biopsy at Visit 4 (Day 3 to 7 post-Tc 99m tilmanocept administration) in accordance with institutional standard operating procedures (SOPs).

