8.5.2 Biopsy Procedure

Subjects will undergo a synovial biopsy of a single joint in the hand or wrist. The synovial biopsy will be performed by a trained member of the clinical study team. Biopsy samples (approximately 12) will be obtained via an 18- or 19-gauge ultrasound-guided quick core biopsy needle and immediately prepared for pathology assessment. Biopsy procedures including subject preparation, tissue harvest, and post-procedure care will be completed in accordance with institutional SOPs.

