### Calculating Global TUV

For each independent blind reader, determine the average  $TUV_{joint}$  and 95% prediction interval of both the anterior and posterior views of the wrists, MCPs, and PIPs in healthy individuals. For all following calculations, reader specific average  $TUV_{joint}$  and 95% prediction intervals will be used.

For each RA subject do the following.

**Step 1:** Calculate  $TUV_{joint}$  for each of the 22 DAS28 joints for which data are collected.

*Step 2:* Identify all imaged joints with  $TUV_{joint} >$  upper limit of normal for the anatomically similar joint and view. These will be referred to as inflamed joints (IJ). Each joint has an anterior and posterior view: a joint is considered an IJ if either view has a  $TUV_{joint}$  higher than the upper bound from the normative data set.

*Step 3:* Calculate the macrophage-involved contribution (MI) to  $Tc\ 99m$  tilmanocept localization for each IJ. This is done by expressing the TUV for the IJ as a fractional change from the mean TUV for the anatomically equivalent joint and view. That is, if  $TUV_{joint}$  and  $\bar{H}_{joint}$  represent the joint and view specific TUV and the mean TUV for the anatomically equivalent joint and view from the normative data set respectively, the macrophage contribution to TUV is  $MI_{joint}$ :

$$MI_{joint} = \frac{TUV_{joint} - \bar{H}_{joint}}{\bar{H}_{joint}}.$$

*Step 4:*  $TUV_{global}$  is the total of the macrophage-involved contributions for the IJs. (Note that  $MI_k$  is effectively 0 if  $TUV_{joint}$  is less than or equal to the upper limit of normal from the normative data set.) That is,

$$TUV_{global} = \sum_{\text{All IJs}} MI_{IJ},$$

$$TUV_{global} = \sum_{k=1}^{22} MI_k.$$

It is presumed that the presence of radiotracer uptake for a joint indicates the presence of activated macrophages. The use of the term “localization” is synonymous with radiotracer uptake.

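### Eligibility and the biopsy text accept any hand or wrist joint, but the biopsy-selection table covers only MCP and wrist joints, so a PIP-only subject can be dosed and imaged with no table option.

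*Protocol*

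**What the plan says.** Four parts of the protocol use the wide wording.

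- Inclusion criterion 9 (synopsis and Section 4.2): "The subject has a hand or wrist joint with a minimum ultrasound gray-scale synovitis score of 2".
- Section 7.1.1, after calling for an ultrasound of the hands and wrists: "Subjects must have at least 1 joint with a minimum gray-scale synovitis score of 2". It sets no restriction on joint type.
- Section 8.5.1, opening prose: "All subjects will undergo a synovial biopsy of a selected hand or wrist joint".
- Section 8.5.2: "Subjects will undergo a synovial biopsy of a single joint in the hand or wrist".

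The selection table uses narrower wording. In Table 4 of Section 8.5.1, Option 1 begins "The subject has only 1 MCP joint or wrist joint with an ultrasound gray-scale synovitis score of" at least 2, and Option 2 begins "The subject has 2 or more MCP and/or wrist joints with an ultrasound gray-scale synovitis score of" at least 2. There is no third option. Table 1 of the protocol synopsis and Table 1 in SAP Section 1.1 carry the same two options.

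The Visit 4 instruction (protocol Section 7.1.4) ties the procedure to the table: "Ultrasound-guided synovial tissue biopsy of selected joint in accordance with" Table 4. SAP Section 1.2 does the same with its Table 1.

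PIP joints are imaged and measured. SAP Section 2.5 builds its normal ranges from "anterior and posterior views of the wrists, MCPs, and PIPs in healthy individuals" and then calculates TUV for 22 DAS28 joints in each RA subject.

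**The concern.** The rule that lets a subject in and the rule that chooses the joint do not cover the same joints. The mismatch is fixed by the screening ultrasound, before dosing, but as the text stands it takes effect only at the biopsy visit, after the subject has received the radiotracer.

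Two things are at stake. The first is a subject who is exposed and imaged but has no joint that the table selects. The second is the selection rule itself. When several joints qualify, the rule alternates between the highest and the lowest TUV and so decides which TUV values enter the primary correlation. If it is unclear which joints count as qualifying, it is also unclear which subjects enter that alternation.

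**Working it through.** No sample-size or power figure is involved. The check is a count of joints and a comparison of the rules.

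**Step 1. Which joints are measured.** The DAS28 form in Appendix 4 lists, for both sides together, 2 shoulders, 2 elbows, 2 wrists, 10 MCPs, 10 PIPs and 2 knees: 2 + 2 + 2 + 10 + 10 + 2 = 28. Imaging covers the hands and wrists only. Removing shoulders, elbows and knees leaves 28 − 6 = 22, which reproduces the SAP's 22 joints: 2 wrists + 10 MCPs + 10 PIPs.

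**Step 2. Which joints the table covers.** Both options name MCP and wrist joints: 10 + 2 = 12 of 22. The remaining 10, all PIPs, appear in neither option.

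**Step 3. Subject types under the two wordings.**

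| Joints scoring at least 2 | Criterion 9 and Section 7.1.1 | Prose of 8.5.1 and 8.5.2 | Selection table |
|---|---|---|---|
| One MCP or wrist, no PIP | Eligible | Biopsy that joint | Option 1 |
| Two or more MCP/wrist, no PIP | Eligible | Choose by TUV | Option 2 |
| PIP only | Eligible | A PIP biopsy is allowed | No option |
| One MCP or wrist and one PIP | Eligible | Two qualifying joints, so choose by TUV | Option 1, no use of TUV |

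No exclusion criterion in Section 4.3 removes the third type.

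**Step 4. What follows for a PIP-only subject.** If otherwise eligible, the subject is injected and imaged on Day 0; Section 8.7.1.4 gives the effective dose as 2.7 mSv. At Visit 4 there are two branches.

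- No biopsy. The ITA definition (protocol Section 9.5.1, SAP Section 2.2) requires one, and PP is a subset of ITA. The subject counts for safety only.
- A PIP biopsy under the prose. ITA sets no condition on joint type, so the subject stays in the primary set if the assay values are valid. The joint has, however, been chosen outside the table that Section 7.1.4 invokes, and Section 3.3 requires strict adherence.

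**Step 5. What follows for the mixed subject.** On the table's wording the MCP or wrist joint is taken under Option 1 and the alternation does not move. On the prose, more than one joint qualifies and TUV decides. That could select the PIP, and it could use one highest or lowest place, which would reverse the assignment of the next Option 2 subject.

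**The case against.** Several points on the other side are fair.

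- **Hand joint is not defined.** Exclusion criterion 5 lists finger, hand and wrist separately, so a site might read criterion 9 as leaving out finger joints. This is arguable. But the documents treat the PIPs as part of imaging the hands and wrists, and nothing in criterion 9 or Section 7.1.1 excludes them.
- **The prose permits a PIP biopsy.** This stands. A reader might infer that a PIP-only subject can never be biopsied or can never yield a primary data point. The documents do not support that: Sections 8.5.1 and 8.5.2 would allow the biopsy, and the subject could remain in ITA. The gap lies in the table and in the instruction to follow it.
- **Precision.** A reader might infer that the primary correlation loses a calculable amount of precision. The documents do not support that either. Section 8.1.1 counts 12 to 24 evaluable subjects. Section 9.4 counts joints, sets a floor of 12, and already allows for biopsies failing in about 15% of cases. The interim analysis waits for 4 subjects in each pathotype, and pathotype is read from biopsy tissue. An unbiopsied subject would not count towards these numbers and would chiefly cost one more enrolment.
- **Frequency.** The documents give no share of PIP-only or mixed subjects. Given a DAS28 of at least 3.2 and an ACR/EULAR score of at least 6, PIP-only subjects could be very rare.
- **Text not available.** The workflow figure in Appendix 2 could not be read and may address joint selection. It would not remove the conflict between the written sections and the table.

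**Conclusion.** The contradiction is real and the plan is wrong as written on this point. The severity is minor. Eligibility, screening and the biopsy prose accept any hand or wrist joint with a score of at least 2; the table that Visit 4 must follow covers 12 of the 22 measured joints. A PIP-only subject can reach the biopsy visit with no table option, and a subject with one qualifying MCP or wrist joint and one qualifying PIP can be handled in two ways.

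The size is best stated per subject. Each PIP-only subject who is not biopsied means one exposure of 2.7 mSv without a primary data pair, and probably one replacement enrolment. Each PIP-only subject who is biopsied means a joint chosen outside the table. No expected number can be given. The conclusion rests on reading hand joint to include the PIPs, as the imaging and TUV sections do.

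**What to change.** Reconcile criterion 9 (synopsis and Section 4.2), Section 7.1.1, Sections 8.5.1 and 8.5.2, protocol Tables 1 and 4 and SAP Table 1 so that all name one set of joints. Which joints belong in the set is for the sponsor and the investigators to decide. Whatever the set, two conditions should hold:

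1. Every subject who passes the screening ultrasound has a table option, and this is confirmed before dosing.
2. The table states which joints count when deciding between Option 1 and Option 2, and therefore which subjects take a place in the highest/lowest alternation.

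The cost is a wording amendment. If eligibility is narrowed to match the table, there may be a few more screen failures. If the table is widened to match eligibility, its options need rewording or an addition. No change to the sample size or the analysis follows from this point.
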